4.0 Study Design

One cycle equals 28 days.

This study is an open-label, two-arm or possibly 3-arm, phase II trial. CPX-351 is administered as approximately a 90-minute infusion on days 1, 3, and 5 with one study arm receiving 50 units/m² and the other receiving 75 units/m². Both the 50 and the 75 unit/m² dose levels are considered to have acceptable safety based on observations from a pair of randomized Phase II studies conducted in adult patients, where the observed 60-day mortality results in patients considered fit for intensive chemotherapy and with no prior history of stem cell transplant, was observed to be reduced compared to control.

Patients with newly diagnosed AML who are predicted to be at high risk (30-50%) for induction mortality (death by day 60) are eligible. Every patient entered must have at least one AML-related factor (adverse cytogenetics, secondary AML, MDR phenotype, etc.) that contributes to elevated risk of induction mortality. Patients may or may not have patient-related factors (poor performance status, co-morbidities, poor organ function, etc.) that also contribute to elevated risk of induction mortality. 30 patients will be randomized with a 1:1 ratio to the two dose arms with 15 patients per arm to assess for safety and efficacy. If safety is demonstrated for both of the sub-MTD dose levels, and escalation is deemed feasible above 75 units/m², a cohort of 15 patients will be studied at 100 units/m², the MTD dose level. The latter dose (i.e., 100 units/m²) was found safe and an additional 25 patients will be enrolled at this dose (for a total of 40 evaluable patients) to define efficacy at this standard dose.

At the end of the study a single dose level will be confirmed to have acceptable safety if the observed rate of dose limiting toxicity (DLT) is <5 DLT/15 patients.<33%). Dose limiting toxicity is defined as induction mortality (death occurring during the first 60 days from start of study therapy), grade 3 or 4 non-hematologic toxicity, or dose limiting

hematologic toxicity at least possibly related to the study drug occurring during the first 60 days from the start of study therapy (i.e., during the first cycle of therapy).

For non-hematologic toxicity the following are counted as dose limiting toxicities only under the conditions noted:

- Liver toxicity: Grade 4, related to the study drug, not resolving to grade 2 within 7 days.

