10.0 Statistical Considerations(16, 17)

General Description:

This is a Phase II study of CPX-351 Liposome Injection in newly diagnosed AML patients with high risk of induction mortality. Two dose levels (50 units/m² and 75 units/m²) of CPX-351 will be studied initially. The primary objective is to evaluate treatment response. The efficacy outcome is CR or CRi within two induction cycles. A maximum of 30 patients will be equally randomized to the two dose levels. A Bayesian method by Thall et al (1995)

will be used for futility and toxicity monitoring. After 15 patients have been accrued to each dose level, an assessment of overall safety/dose limiting toxicities and efficacy will be made and one dose level will be chosen for further study. OR if both dose levels are safe and further dose escalation seems possible, one additional cohort with a dose of 100 units/m² will be open. A maximum of 15 patients will be enrolled in this arm and the same toxicity and futility monitor rules will be applied. After 2 or 3 dose levels have been studied, one dose levels will be chosen for further study. An expansion cohort of 10 patients will be treated at the dose level with a favorable response and/or toxicity profile for further evaluation for safety and efficacy. Consequently, the preferred dose level has 25 patients evaluable.

Additional 25 patients will be added to the arm with the dose of 100 units/m², the sample size for this arm will be up to 40, and the maximum number of patients for all three arms will be up to 80.

Multc Lean software version 2.1 developed in the Department of Biostatistics MDACC was used for the study design.

The study will monitor futility and toxicity, and the monitoring rules will be applied to each dose separately. If study in one of the two doses is stopped early due to futility or excessive toxicity, all the future patients will be enrolled in the open dose arm (i.e., without randomization). In the case the lower dose (50 units/m²) has been shown to be too toxic at an interim look (thus stop further patient enrollment) the higher dose (75 units/m²) will also stop accrual.

Futility monitoring:

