Treatment success is defined as achievement of CR or CRi. We will accrue a maximum of 15 patients at each dose level and test the null hypothesis that the true response is at most 5% (meaning little or no activity) versus the alternative hypothesis that the true response is 30% or greater, independently in each treatment arm. Assuming that the success rate is binomially distributed, this design with 15 patients in each arm has 87% power and a one-sided type I error rate of 0.05 using an exact test.

To monitor futility, the study in one dose level will be stopped early if the data in that dose level suggest that:

$$\Pr(\theta_E < 0.25 + \theta_s | \text{data}) > 0.95$$

That is, if at any time during the study we determine that there is a greater than 95% chance that the response rate is less likely to improve by 25% than the null hypothesis in one dose level, we will terminate the enrollment in that dose. Here θ_E represents the response rate for experimental drug in this study and θ_s represents the response rate for the standard practice (null hypothesis). We assume that θ_s has a distribution of beta (10, 190) to reflect the information on 200 patients for the historical data, which has a mean response rate of 0.05 and a variance of 0.0002. We also assume that θ_E has a non-informative flat prior beta(0.1, 1.9) with mean of 0.05 and variance of 0.0158.

The futility stopping boundaries for the overall response based on these assumptions and monitoring condition is shown in table 7. For example, accrual will be stopped in one dose if there is no response observed in the first 5 patients treated in that dose.

The toxicity monitoring/efficacy summary will be submitted to the IND Office Medical Monitor ([name]) for every 5 subjects treated in each Arm (per Table 7, 8, 11 & 12).

Table 7: Stopping boundaries for futility monitoring for the initial cohort of each dose (n=15)

# Patients (in complete cohorts of 5) (inclusive)	Stop the enrollment in one dose if there are this many responses total in that dose:

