# DLTs (inclusive)	
5	4-5
10	6-10
15	Always stop with this many patients

The operating characteristics for this design are presented in table 9. If the enrollment in one dose continues until 15 patients are evaluated in each arm and 5 CR or CRi are observed, then the 95% credible interval for the response rate would be (11.6%, 47.7%).

Table 9: Operating characteristics of the initial cohort of each dose (n=15)

True CR+CRi Rate	True DLT Rate	Early Stopping Probabilities	Average sample size treated
0.05	0.1	0.931	6.47
0.05	0.2	0.932	6.46
0.05	0.33	0.938	6.39
0.05	0.5	0.959	6.12
0.1	0.1	0.784	88.13
0.1	0.2	0.787	8.10
0.1	0.33	0.804	7.94
0.1	0.5	0.872	7.30
0.2	0.1	0.462	11.1
0.2	0.2	0.468	11.0
0.2	0.33	0.512	10.66
0.2	0.5	0.681	9.33
0.3	0.1	0.229	13.01
0.3	0.2	0.237	12.95
0.3	0.33	0.30	12.5
0.3	0.5	0.543	10.67
0.3	0.6	0.735	9.08
0.4	0.1	0.098	14.11
0.4	0.2	0.108	14.04
0.4	0.33	0.181	13.50
0.4	0.5	0.465	11.42
0.4	0.6	0.691	9.61

If three dose arms continue until 15 patients in each arm evaluated, the toxicity profile and response will be summarized for them. The dose chosen for further study will be the dose with the highest CR+CRi rate, provided that toxicity profile are also acceptable. The probability of correctly selecting the superior dose for different success rate scenarios in the three arms is summarized in table 10 below [Simon R et al 1985].

Table 10: Probability of the best arm being chosen

True Response rate in Superior Dose	True Response rate in inferior Dose 1	True Response rate in inferior Dose 2	Probability of the best arm is chosen

30%	10%	10%	86%
30%	15%	15%	71%
40%	25%	25%	63%
40%	30%	25%	56%
40%	30%	30%	50%
50%	25%	25%	83%
50%	30%	25%	78%
50%	30%	30%	73%
50%	40%	30%	59%
60%	25%	25%	94%
60%	30%	25%	91%
60%	30%	30%	89%
60%	40%	30%	79%
60%	50%	30%	63%

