	# Toxicities (inclusive)
5	4-5
10	6-10
15	8-15
20	10-20
25	Always stop with this many patients

Expansion of arm with the dose of 100 units/m²

Up to additional 25 patients will be enrolled in this arm, thus total sample size for this arm is up to 40. Assuming that the success rate is binomially distributed, 40 patients will have has 99% power to detect a difference of 5% vs. 30% in success rate at a one-sided type I error rate of 0.05 using an exact test.

Similar futility and toxicity monitoring rules listed above will also be applied for the expansion of arm with 100 units/m². That is, the trial will be stopped early if

$$\Pr(\theta_E < 0.25 + \theta_S | \text{data}) > 0.98 \text{ for futility}$$

or

$$\Pr(T_E > 0.33 | \text{data}) > 0.95 \text{ for toxicity}$$

where θ_E represents the response rate for experimental drug in this study and θ_S represents the response rate for the standard practice (null hypothesis). T_E represents DLT rate. For trial simulation, we use the same assumption for prior distributions listed above for each parameter. That is, θ_S has a prior distribution of beta (10, 190), θ_E has a non-informative flat prior beta(0.1, 1.9), and T_E has a prior distribution of beta (0.66, 1.34).

Table 12 and 13 present the corresponding stopping boundary and operating characteristics (OCs).

Table 12: Stopping boundaries for futility and toxicity of the expansion cohort with the dose of 100 units/m²

N patients evaluated	Stop for toxicity if >= this number of patients experience DLT	Stop for futility if <= this number of patients achieve CR/Ci
5	4-5	0
10	7-10	0
15	9-15	0-1
20	11-20	0-2
25	13-25	0-3
30	15-30	0-4
35	17-35	0-5
40	19-40	0-6

Table 13: OCs of the expansion cohort with the dose of 100 units/m²

True CR+CRi Rate	True DLT Rate	Early Stopping Probabilities	Average sample size treated
0.05	0.1	0.9965	8.16
0.05	0.2	0.9965	8.14
0.05	0.33	0.9969	7.99
0.05	0.5	0.999	7.26
0.1	0.1	0.9294	13.16
0.1	0.2	0.930	13.10
0.1	0.33	0.9372	12.63
0.1	0.5	0.9803	10.19
0.2	0.1	0.5119	25.54
0.2	0.2	0.5156	25.39
0.2	0.33	0.5654	24.00

0.2	0.5	0.8637	16.36
0.3	0.1	0.2029	33.50
0.3	0.2	0.209	33.30
0.3	0.33	0.2903	31.31
0.3	0.5	0.7774	20.23
0.4	0.1	0.0817	37.19
0.4	0.2	0.0887	36.96
0.4	0.33	0.1824	34.70
0.4	0.5	0.7436	22.12
0.4	0.6	0.9612	14.02

Statistical methods:

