Data analysis will be performed using SAS or S-plus, as appropriate. For each arm, the CR/CR_i rate and the DLT rate will be estimated with 95% confidence intervals. The intent-to-treat patients will be used for the primary efficacy analysis, patients who lost-to-follow up in the first 2 cycles will be treated as failures. Patients who received at least one dose of the treatment drug will be evaluable for toxicity outcomes. In addition, Fisher's exact test will be used to compare the response rate and toxicity rate between the two dose levels. For the exploratory objectives, Fisher's exact test will be used to compare immune responses between different doses of CPX-351. Two-sample t test or ANOVA or Fisher's exact test will be used to check the association between Troponin - T and cardiotoxicity, and t test or ANOVA will be used to compare the apoptosis of ex-vivo cultured leukemia cells.

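### The 87% power for 15 patients per arm ignores the plan's own futility stops; under those stops it is about 74% and cannot exceed 77.1%

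*Combined protocol and SAP*

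**What the plan says.** Section 10.0, Futility monitoring, sets out to "test the null hypothesis that the true response is at most 5" per cent, against an alternative of 30% or more, separately in each arm with at most 15 patients. It then says that "this design with 15 patients in each arm has 87% power and a one-sided type I error rate of 0.05 using an exact test". No critical value is given.

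The same subsection makes stopping mandatory: "accrual will be stopped in one dose if there is no response observed in the first 5 patients treated in that dose". Table 7 adds a second look, with a stop at 0–1 responses in 10. Table 8 adds toxicity stops at 4 or more DLTs in 5 and at 6 or more in 10. Below Table 8 the plan says: "The operating characteristics for this design are presented in table 9". Table 9 gives early-stopping probabilities at 30% response of 0.229, 0.237 and 0.30 for true DLT rates of 10%, 20% and 33%.

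For the 100 units/m² arm, the General Description says: "A maximum of 15 patients will be enrolled in this arm and the same toxicity and futility monitor rules will be applied". Section 4.0 reports that this dose "was found safe and an additional 25 patients will be enrolled at this dose". The expansion subsection of Section 10.0 then says that "40 patients will have has 99% power to detect a difference of 5% vs. 30% in success rate". Table 12 lists looks from patient 5 to patient 40, and Table 13 gives early stopping of 0.2029 at 30% response and 10% DLT.

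**The concern.** The power sentence and Table 9 both claim to describe this design, and they cannot both do so. A design that closes an arm more than a fifth of the time under the alternative cannot have 87% power, because a closed arm cannot later be declared a success.

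The power figure is the plan's justification for 15 patients per arm on the primary endpoint. A reader who takes it at face value believes that a dose with a true 30% response is missed about one time in eight. Under the plan's rules it is about one time in four.

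At 40 patients the difficulty is different. The reader cannot tell whether 99% refers to the whole arm or only to the extension after the first 15 patients.

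**Working it through.** **Inputs.** Null 5%, alternative 30%, maximum 15 patients, one-sided 0.05, exact test (Futility monitoring); stops at 0/5 and 0–1/10 (Table 7); toxicity stops at 4 or more of 5 and 6 or more of 10 (Table 8); Tables 9, 12 and 13 for comparison. Where toxicity enters, response and DLT are taken as independent.

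**1. Reproduce the plan's figure.** Single-stage exact binomial, n = 15:

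| Success if at least | Type I error (5%) | Power (30%) |
|---|---|---|
| 2/15 | 17.1% | 96.5% |
| 3/15 | 3.6% | 87.3% |
| 4/15 | 0.5% | 70.3% |

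Only 3/15 gives 87% with type I error at or below 0.05. The cut-off is inferred in this way, since the plan does not state one.

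**2. Add the Table 7 looks at a true rate of 30%.**

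- Stop at 5: 0.7^5 = 0.1681. Power is already at most 83.2%.
- Stop at 10 (one response in the first 5, none in the next 5): (5 × 0.3 × 0.7^4) × 0.7^5 = 0.3602 × 0.1681 = 0.0605.
- Reach 15: 1 − 0.1681 − 0.0605 = 0.7714. This is the ceiling for any final cut-off. Table 9 agrees: 1 − 0.229 = 0.771.
- Reach 15 with fewer than 3 responses (exactly 2 at patient 10 after at least 1 in the first 5, then none in the last 5): 0.1816 × 0.1681 = 0.0305.
- Power with 3/15: 0.7714 − 0.0305 = 0.741. The same calculation at 5% gives a type I error of 0.024.

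**3. Add the Table 8 toxicity stops.** Power is 74.0%, 73.3% and 67.2% at DLT rates of 10%, 20% and 33%. The enumeration reproduces Table 9: 0.229, 0.237 and 0.30 at 30% response, and 0.931 at 5% response with 10% DLT.

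**4. The 100 units/m² arm, n = 40, true rate 30%.** Futility stops only, unless stated.

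- Fixed sample: 99.7% for 5 or more of 40 (type I error 4.8%) and 99.1% for 6 or more (1.4%). The stated 99% is a fixed-sample figure.
- Table 12 applied from patient 1: early stopping 0.2025, power 79.7%. Adding toxicity stops at 10% DLT gives 0.2029 and an average of 33.50 patients, exactly as in Table 13. Of the 0.2025, 0.1782 (88%) comes from the looks at 5 and 15, that is, from within the first 15 patients.
- Table 7 for the first 15, then Table 12: power 75.4% unconditionally. Given that the arm passed the Table 7 looks, it is 0.7544 / 0.7714 = 97.8%, with later early stopping of 2.2% and an average sample size of 39.7.
- The last row of Table 12 marks 0–6 of 40 as futility. If success therefore needs 7 or more, the figures become 97.6% (fixed), 97.5% (conditional), 75.2% (Table 7 then Table 12) and 79.5% (Table 12 throughout).

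**5. The cut-off in Section 4.0.** That section calls 3 or fewer responses in 15 (20% or less) non-efficacious, yet allows an arm to be recommended if its rate is 20% or more. An arm with 3/15 meets both descriptions. If 4/15 were the success criterion, power would be 70.3% fixed-sample and 63.4% with the Table 7 stops.

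**The case against.** The strongest reply is that 87% is correctly computed for what the sentence literally names: 15 patients, a binomial outcome and an exact test. It comes before the monitoring rule is introduced, and Table 9 then shows how often arms stop. On this view only a label is missing. That is fair as to how the figure arose. It does not rescue the sentence, which assigns the power to the design. Table 9 reports stopping rather than power, so a reader has to notice the conflict and work out the answer.

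The second reply is that little depends on it. Statistical methods plans estimation only: the CR/CRi rate and "the DLT rate will be estimated with 95% confidence intervals". It lists no test against 5%. Doses are chosen by the highest response rate, and Section 4.0 suggests that the 15-patient stage is already past. This stands, and it confines the point to the sample-size justification.

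Third, the 74% rests on an inferred cut-off. True, but the 77.1% ceiling does not depend on it, and the ceiling alone rules out 87%.

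Fourth, the 99% at 40 patients is close to the conditional 97.8%, Table 13 is a coherent whole-arm calculation, and the plan tabulates no scheme with Table 7 followed by Table 12. All of this stands. The remaining defect there is that the power and Table 13 are on different bases and neither basis is stated. The clash at 3/15 in Section 4.0 is a separate inconsistency. It matters here only because 3/15 is the cut-off that reproduces 87%.

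**Conclusion.** The point holds. The 87% is a fixed-sample value. Under the mandatory Table 7 stops, power at a true 30% response is at most 77.1% for any cut-off and 74.1% for 3 of 15, a shortfall of about 13 percentage points. Type I error falls to 2.4%, so the stops cost power and do not inflate false positives. The 74.1% assumes the inferred cut-off and futility stops only; toxicity stops lower it to 67.2% at a 33% DLT rate if response and DLT are independent.

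At 40 patients, 99% is nearly right for an arm that has passed its first 15 patients (about 98%), but well above the whole-arm value (about 75% to 80%). On the conditional reading, it is Table 13 that does not describe the expansion.

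This should be corrected because it misstates the design's sensitivity for the primary endpoint. It alters no boundary, sample size or patient-level action.

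**What to change.** 1. For 15 patients per arm, state the success cut-off. If it is 3 of 15, give the power as about 74% with a type I error of about 2.4% under the Table 7 stops. If 87% is kept, label it as fixed-sample, before futility stopping, and refer to Table 9.
2. For the 100 units/m² arm, state the basis of the power. Either give about 98%, conditional on passing the Table 7 looks in the first 15 patients, and recompute Table 13 from that point; or give the whole-arm figure, about 75% with Table 7 then Table 12, or about 80% with Table 12 from patient 1. Say which looks govern the first 15 patients, and whether the 40-patient row of Table 12 defines success.
3. Reconcile the two statements in Section 4.0 at 3/15, and say whether that rule is the success criterion behind the power.

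The cost is the wording of a few sentences and a relabelled or recomputed Table 13. No patients are added and no boundary changes; the stated power becomes less favourable.

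### The futility prior is not flat: it starts at 0.945 against a 0.95 cutoff, the written rule contradicts the cohort looks in Tables 7 and 9, and the stated 87% power ignores those looks

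*Combined protocol and SAP*

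**What the plan says.** Section 10.0 (Futility monitoring) tests, separately in each dose arm of 15 patients, whether "the true response is at most 5% (meaning little or no activity) versus the alternative hypothesis that the true response is 30% or greater". It states that "this design with 15 patients in each arm has 87% power and a one-sided type I error rate of 0.05 using an exact test".

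It then adds a Bayesian stopping rule: enrollment in a dose ends if Pr(θ_E < 0.25 + θ_S | data) > 0.95. The prose applies this "if at any time during the study we determine that there is a greater than 95% chance" and names no minimum number of patients. The standard rate θ_S "has a distribution of beta (10, 190) to reflect the information on 200 patients for the historical data". The experimental rate θ_E has a "non-informative flat prior beta(0.1, 1.9) with mean of 0.05 and variance of 0.0158".

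Table 7 gives boundaries in complete cohorts of 5: stop at 0 of 5, or at 0 or 1 of 10. The worked example is no response in the first 5, and summaries go to the Medical Monitor after every 5 patients in an arm. Table 9 reports early stopping of 0.229 and an average of 13.01 patients at a true response of 0.30 and a DLT rate of 0.1.

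For the expansion at 100 units/m², Section 10.0 repeats the same prior under the same label, raises the futility cutoff to 0.98, and gives boundaries at multiples of 5 in Table 12.

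**The concern.** A reader told that a prior is flat and non-informative expects the data to decide when an arm closes. Here the prior sits almost on the stopping threshold, so very little data is needed to cross it. Combined with a rule that may be evaluated at any point, the text describes a design very different from the one tabulated. A stopping rule decides whether an arm closes, so its prose and its table should give the same answer. Separately, the power is quoted for a fixed sample of 15, although the same section allows the arm to close at 5 or 10.

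**Working it through.** **Inputs**, all from Section 10.0: θ_E ~ Beta(0.1, 1.9); θ_S ~ Beta(10, 190); margin 0.25; cutoff 0.95 (0.98 for the 100 units/m² expansion); Table 7 boundaries; null 5%, target 30%, n = 15.

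**1. The prior.** Mean = 0.1/2 = 0.05. Variance = (0.1 × 1.9)/(2² × 3) = 0.0158, as stated. Its weight is 0.1 + 1.9 = 2 patients. About 69% of its mass lies below a 1% response and 81% below 5%; only 5.5% lies above 30%. A flat Beta(1,1) has variance 0.0833.

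**2. Reproducing Table 7.** After r responses in n patients, θ_E ~ Beta(0.1 + r, 1.9 + n − r). The futility probability is this distribution's CDF at θ_S + 0.25, averaged over the Beta(10, 190) density.

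| Data | Futility probability | Above 0.95? |
|---|---|---|
| 0/5 | 0.996 | yes |
| 1/5 | 0.858 | no |
| 1/10 | 0.975 | yes |
| 2/10 | 0.870 | no |

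Table 7 reproduces exactly.

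**3. The same formula where the prose allows it.**

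| Data | Futility probability |
|---|---|
| no patients | 0.945 |
| 0/1 | 0.971 |
| 0/2 | 0.983 |
| 1/2 | 0.608 |

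The prior alone is 0.005 short of the cutoff, and a first patient who does not respond crosses it. Under the 0.98 cutoff of the expansion, 0/1 does not cross but 0/2 would.

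**4. Stopping at a true response of 30%.**
- *Applied after every patient.* The first patient alone stops the arm with probability 0.70. Exact recursion over patients 1 to 14 (stop at 0 responses for n = 1–8, at most 1 for n = 9–13, at most 2 for n = 14) gives 0.727 in total, with an average of 5.1 patients.
- *Looks at 5 and 10 (Table 7).* 0/5: 0.7⁵ = 0.1681. One response in the first five and none in the next five: 5 × 0.3 × 0.7⁴ × 0.7⁵ = 0.3602 × 0.1681 = 0.0605. The total is 0.2286, with an average of 13.0 patients.

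Adding the toxicity boundaries at a DLT rate of 0.1 gives 0.2290 and 13.01, which are Table 9's figures. Table 9 reproduces only with looks at 5 and 10.

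**5. Power.** P(at least 3 of 15 at 30%) with no interim look = 0.873, the stated 87%; the exact type I error of that cutoff is 0.036. The Table 7 looks remove arms that would have reached 3:
- stopped at 0/5, then at least 3 of the next 10: 0.1681 × 0.6172 = 0.1037
- stopped at 1/10, then at least 2 of the next 5: 0.0605 × 0.4718 = 0.0286

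Power with the tabulated looks = 0.8732 − 0.1037 − 0.0286 = 0.7409, or 74.1%. If the rule were applied after each patient it would be 27.3%.

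**The case against.** The strongest reply is that the tabulated design is the operative one. Table 7, the 0-of-5 example, reporting every 5 patients and the reproduction of Table 9 all point to looks at 5 and 10. This stands. A reader might infer that arms really would close after one patient, or that 73% of good arms are lost. The documents do not support that: those figures describe the prose rule, not the design that was simulated.

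A reader might also infer that the mislabelled prior hides an aggressive rule. Table 9 prints the 0.229, and the section prints the prior's parameters, mean and variance. Early stopping of about 23% at the target rate is therefore a disclosed choice, set against 93% early stopping and an average of 6.5 patients at a true 5%.

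A third tempting reading is that the prior alone creates the Table 7 boundaries. Under Beta(1,1), 0/5 gives 0.882 and 1/10 gives 0.886, and neither stops. But a prior of the same weight centred on the 30% target, Beta(0.6, 1.4), gives 0.953 at 0/5 and still stops; Beta(0.5, 0.5) gives 0.947, just short. The 0/5 boundary accounts for 16.8 of the 22.9 percentage points. Only the 1/10 boundary clearly depends on the prior (0.936 and 0.925 under those two alternatives).

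Finally, the 87% can be defended as a fixed-sample calculation. It is correct as such, but the text attributes it to this design, which includes the interim looks.

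**Conclusion.** The point holds as three errors in the text, not as a fault in the tabulated boundaries. The prior is wrongly described: it is centred on the null rate and carries a futility probability of 0.945 before any patient is treated. The prose rule is met at 0/1 (0.971) and contradicts Tables 7 and 9: 72.7% against 22.9% stopping at a true 30%. The power under the Table 7 looks is 74.1%, about 13 points below the stated 87%.

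These results assume independent binomial responses, success defined as at least 3 of 15 (the cutoff that reproduces the stated 87%), binding futility stops, and no toxicity stops in the power figure. Toxicity stops could only lower it further. In the 100 units/m² expansion the problem is milder, because one non-responder does not cross 0.98.

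**What to change.** 1. In the futility rule, replace the open-ended timing with evaluation after 5 and after 10 evaluated patients, as in Table 7. For the 100 units/m² expansion, tie the rule to the cohort-of-5 looks in Table 12.
2. In both places, replace the non-informative flat label with: prior centred at the 5% null rate, effective sample size 2, prior futility probability 0.945.
3. Restate the power for 15 patients per arm as about 74% with the Table 7 futility looks, and 87% only without interim stopping.

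All three are wording changes. No boundary or operating characteristic in Tables 7, 9, 12 or 13 changes. Section 4.0 says the 100 units/m² dose was found safe and is being expanded, so the initial looks at the first two doses appear to be past. For those arms the correction mainly affects how the design is reported.

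Moving to Beta(1,1) is not required. With looks at 5 and 10 it would leave 0/10 as the only boundary and bring power to 86.9%. But early stopping at a true 5% would fall from 93% to 60%, and the average number treated there would rise from 6.5 to 12.0. That is a design trade-off, not a correction.
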